1.1.2.2. Subcutaneous Golimumab in Juvenile Idiopathic Arthritis

CNTO148JIA3001 was a randomized withdrawal, double-blind, placebo-controlled, parallel-group, multicenter study of BSA-based 30 mg/m² (up to a maximum 50 mg/dose) SC golimumab given every 4 weeks (q4w) in pediatric subjects with active pJIA despite current treatment with MTX. The study population comprised subjects with pJIA receiving MTX, ages 2 to less than 18 years, with at least a 6-month history of pJIA, and active arthritis in ≥5 joints. All subjects received SC golimumab in the active treatment portion of the study from Week 0 through Week 16. At Week 16, JIA ACR 30 responders were randomized to receive placebo or golimumab for 32 weeks; subjects randomized to placebo who experienced flares during this 32-week period had golimumab therapy re-instituted. The placebo-controlled period was through Week 48, and the long-term extension (LTE) was planned from Week 48 through Week 248.

Approximately 170 subjects were planned, and 173 subjects were enrolled into the study. All of the 173 subjects were included in the Week 48 efficacy and safety analyses. Nineteen of the 173 subjects discontinued study agent through Week 16 (due to: lack of efficacy [n = 14]; AEs [n = 4]; withdrawal of consent [n = 1]), and 154 subjects entered randomized withdrawal (76 to placebo and 78 continued golimumab).

The baseline disease characteristics of the 173 enrolled subjects constituted a population with moderate to severe JIA comparable with other clinical studies of anti-TNF α agents in pJIA, with the exception of numerically lower mean and median CRP/ESR levels in CNTO148JIA3001.

The proportion of subjects who were JIA ACR 30 responders at Week 16 was 87.3%. Additionally, the proportion of JIA ACR 50, JIA ACR 70, and JIA ACR 90 responders at Week 16 were 79.2%, 65.9%, and 36.4%, respectively.

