The study did not meet its primary and major secondary endpoints as the proportion of subjects who were JIA ACR 30 responders at Week 16 and did not experience a flare of disease between Week 16 and Week 48 was not significantly different in subjects randomized to continued golimumab treatment between Weeks 16 and 48 as compared with subjects randomized to receive placebo between Weeks 16 and 48 (59% versus 52.6%, p=0.41). All sensitivity analyses and major secondary endpoints demonstrated the lack of statistically significant differences between treatment groups. The Sponsor terminated the LTE of the study early as pre-specified efficacy endpoints were not met.

Post-hoc analyses that evaluated flare rates based on Week 0 CRP levels ranging from 0.1-1.0 mg/dL demonstrated that, in general, among subjects with higher baseline CRP levels, the subjects who received continued golimumab therapy had significantly fewer flare episodes than subjects who were randomized to placebo at Week 16.

When JIA ACR response rates were analyzed based on observed data through Week 48 (using Week 0 as baseline and comparing drug/placebo effect at each visit through Week 48), JIA ACR 30 response rates of 89% to 95.9% and JIA ACR 90 response rates of 53.4% to 56.2% were achieved at Week 48. Improvements in the core sets through Week 48 were similar at all

visits in subjects randomized to golimumab at Week 16 as compared with subjects randomized to placebo at Week 16 and all represented clinically meaningful improvement in disease, eg, median percent improvement of 94.6% and 95.1% in Physician Global Assessment of Disease Activity, and median percent improvement of 90.9% and 100% in the number of active joints.

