Pharmacokinetic (PK) and immunogenicity data were collected through Week 48 in CNTO148JIA3001. In subjects with pJIA who received golimumab 30 mg/m² SC and were randomized to stay on active treatment, median trough golimumab concentrations at Week 12, Week 24, and Week 48 were 1.16 µg/mL, 1.12 µg/mL, and 0.95 µg/mL, respectively, indicating that steady-state levels were maintained though Week 48. Furthermore, steady-state trough golimumab concentrations were similar across different age groups, body weight quartiles, body mass index quartiles, and body weight categories in subjects with pJIA. Overall, these concentrations were similar to the PK exposure observed in the adult active RA population (despite MTX) in C0524T06 treated with SC golimumab, and thus supported the hypothesis that the BSA-based golimumab regimen of 30 mg/m² SC q4w was sufficient to produce concentrations comparable to that seen in the adult RA population who received golimumab 50 mg SC q4w. Further, PK and efficacy analyses showed that similar efficacy (as measured by JIA ACR 30 response, and flare rates) were seen in subjects with pJIA in the 4 subgroups of steady-state trough golimumab concentration quartiles. Additionally, there were no apparent PK differences observed between subjects with and without flares.

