1.4. Sample Size Justification

The sample size determination is not based on statistical considerations. For the purpose of determining sample size of this study, the variability of PK in pediatric populations was considered. The goal is to have a sample size that will be sufficient to build a population PK and, if feasible, an exposure-response model. Additionally, a sample size that will provide information about the safety profile of golimumab IV in children was also taken into consideration.

With these considerations, a sample size of approximately 120 subjects has been chosen assuming that if 20 subjects were to drop out or if they do not provide PK samples, a sample size of approximately 100 subjects is thought to be sufficient to build a population PK model, given the sparse sampling of PK time points, as well as provide 1 year of safety data from approximately 100 subjects.

Assuming that inter-subject coefficient of variation (CV%) of concentration is about 50% (moderate – large variation), a sample size of 100 subjects will be able to provide a 95% confidence interval (CI) with the length about 20% of the mean concentration, i.e., 95% CI \approx Mean×(1 \pm 10%).

The table below provides the length of 95% CI of mean concentration using sample size of 100 subjects with various CV% from 30% (small variation) to 70% (larger variation).

CV %	95% CI
30%	Mean×(1± 5.9%)
40%	Mean×(1± 7.8%)
50%	Mean×(1± 9.8%)
60%	Mean×(1±11.8%)
70%	Mean×(1±13.7%)

Table 1: Length of 95% CI with Sample Size 100 Subjects

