2.4.2. Subgroups for the Summary of Other Efficacy Endpoints

In addition to demographic subgroups of age, gender, race, geographic region, weight, BMI, and BSA the following subgroups will also be used for the summary of JIA ACR30 (Section 5.4.1.1). The subgroups for efficacy analyses include, but are not limited to, the following:

Baseline disease characteristics subgroups

- a. ILAR classification of disease (Systemic onset with polyarticular course with no systemic symptoms, Polyarticular Rheumatoid Factor-negative, Polyarticular Rheumatoid Factor-positive, Oligoarticular extended, Juvenile Psoriatic Arthritis, and Enthesitis-related JIA)
- b. Number of active joints ($<6, \ge 6$ to $<10, \ge 10$)
- c. Number of joints with limited range of motion ($<6, \ge 6$ to $<10, \ge 10$)
- d. CHAQ ($<1, \ge 1$ to $<2, \ge 2$)
- e. CRP (<1.0 mg/dL, and $\ge 1.0 \text{ mg/dL}$ at baseline (Week 0))
- f. CRP (<0.1 mg/dL, and $\ge 0.1 \text{ mg/dL}$ at baseline (Week 0))
- g. Previous joint surgery (yes, no)
- h. Disease duration (<6 months, ≥6 months to <1 year, ≥1 year to <3 years, ≥3 years)

Medication use subgroups:

- a. Prior anti-TNF therapy (yes, no)
- b. Oral corticosteroids (yes, no)
- c. NSAIDs (yes, no)
- d. MTX dose: tertiles
- e. Duration of MTX therapy (<1 year, \geq 1 year to <3 years, \geq 3 years)
- f. Prior DMARDs excluding MTX $(0, 1, 2, \ge 3)$
- g. Concomitant conventional DMARDs use at baseline, excluding MTX $(0, 1, 2, \ge 3)$
- h. Prior biologics, excluding anti-TNFs (yes, no)
- i. Prior JAK inhibitors (yes, no)

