5. EFFICACY

5.1. Analysis Specifications

5.1.1. Level of Significance

No statistical testing will be performed.

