7.1.3. General PK Summaries

PK samples for measuring serum golimumab concentrations will be collected from all subjects at the specified visits as shown in the schedule of events of the protocol. Samples will be collected at Weeks 0, 4, 8, 12, 20, 28, 52, 100, 148, 196 and 244. Two samples, one pre-infusion and another post-infusion, will be collected at Weeks 0, 4, and 12. An additional random PK sample for serum golimumab concentration will be collected from all subjects at any time between Weeks 0 and 8 other than at the time of the Week 0, 4 and 8 visits; this sample must be collected at least 24 hours before or after a study agent infusion.

All PK evaluations will be based on the subjects who receive at least 1 infusion of golimumab (PKE analysis set).

No imputation for missing concentration data will be performed. Pre and post infusion serum concentrations will be summarized separately.

The data analysis of serum golimumab concentrations includes the following:

- Summary of serum golimumab concentrations at each visit
- Summary of serum golimumab concentrations at each visit by body weight quartiles.
- Summary of serum golimumab concentrations at each visit by BMI quartiles.

- Summary of serum golimumab concentrations at each visit by BSA quartiles.
- Summary of serum golimumab concentrations at each visit by age (2 to <6 years, 6 to <12 years, 12 to <18 years).
- Summary of serum golimumab concentrations at each visit by CRP quartiles and CRP categories (<0.1 mg/dL, ≥0.1 mg/dL; <1.0 mg/dL, ≥1.0 mg/dL).
- Proportion of subjects without detectable serum golimumab concentration at each visit.
- Summary of serum golimumab concentrations at each visit by antibodies to golimumab status.
- Median serum golimumab concentrations plotted over time.

In addition, the relationship between serum golimumab concentrations and antibody to golimumab status, safety and efficacy may be explored using graphical displays. Median serum golimumab concentrations will be plotted. Box plots of serum golimumab concentrations will be plotted by percentage subjects who achieved JIA ACR 30 responses.

For summary statistics of serum golimumab concentrations, concentration values below the lower limit of quantification will be treated as zero. Once a subject meets one of the following dosing deviation criteria, the subject's data will be excluded from the by-visit data analyses from that point onwards.

Dosing deviation criteria:

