7.3. Immunogenicity

Blood samples will be collected to examine the formation of antibodies to golimumab at the specified visits as shown in the schedule of events of the protocol. For subjects who discontinue IV study agent administrations, samples will be collected at their safety follow-up visit.

The data analysis of antibodies to golimumab includes the following:

- The antibody status (positive, negative) of subjects will be summarized. For subjects who discontinue IV study agent administrations and complete safety follow-up, a listing of their antibody status will be presented.
- The relationship between antibody to golimumab status and efficacy and safety will be assessed at major assessment time points (Weeks 28, 52 and 252). JIA ACR 30 responses by antibody to golimumab status; infusion reactions by antibody to golimumab status.
- The relationship between antibody to golimumab status at Week 28 and antibody to golimumab status at Week 52 will be explored.
- The onset of antibody to golimumab formation will be summarized
- The duration of antibody to golimumab will be summarized.
- The serum golimumab concentrations by antibody to golimumab status will be presented graphically.

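### SAP 7.3 and 7.1.3 specify only JIA ACR 30 for the antibody and concentration displays; if response is as high as in the sponsor's earlier paediatric study, it separates strata less well than JIA ACR 70 or 90

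*SAP*

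**What the plan says.** SAP 7.3 (Immunogenicity) plans to assess how antibody status relates to efficacy and safety at the main time points. It spells this out as "JIA ACR 30 responses by antibody to golimumab status; infusion reactions by antibody to golimumab status". No other efficacy measure is named, and antibody status is positive or negative.

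SAP 7.1.3 (General PK Summaries) names one display that links concentration to efficacy: "Box plots of serum golimumab concentrations will be plotted by percentage subjects who achieved JIA ACR 30 responses". I read this as box plots split by responder status.

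SAP 2.4.2 attaches its baseline-disease and medication lists to the same endpoint ("the following subgroups will also be used for the summary of JIA ACR30"), but calls the efficacy subgroups non-exhaustive. SAP 5.4.2 derives JIA ACR 30, 50, 70 and 90 over time, and plans all four levels by disease subtype and/or age through Week 52.

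The PK/PD endpoint is left open. Protocol 9.3.3 commits to an exposure-response analysis and Protocol 11.6 to exploring and developing a PK/PD model. SAP 7.2 says concentration-efficacy relations may be explored and reported separately. None of these names an efficacy measure.

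For the subcutaneous paediatric study, Protocol 1.1.2.2 reports: "The proportion of subjects who were JIA ACR 30 responders at Week 16 was 87.3" (per cent). JIA ACR 50, 70 and 90 at the same visit were 79.2%, 65.9% and 36.4%.

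**The concern.** When nearly all children respond, a responder split has few non-responders and carries little information about how much benefit each child had. Immunogenicity is a secondary objective (Protocol 2.1), and efficacy data are collected partly for a supportive exposure-response assessment (Protocol 3.2.3). Similar JIA ACR 30 rates across strata are then weak evidence that antibodies or low exposure do not matter.

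There is a precedent for relying on this endpoint. In the subcutaneous study, Protocol 1.1.2.2 reports that "similar efficacy (as measured by JIA ACR 30 response, and flare rates) were seen in subjects with pJIA in the 4 subgroups" of trough concentration. JIA ACR 50, 70 and 90 sit further from the ceiling in the same data and are already derived, so leaving them out of these two displays gives up sensitivity for no saving in data collection.

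**Working it through.** **The plan's own precision figure.** SAP Table 1 gives ±9.8% for the mean concentration at CV 50% and n = 100. Check: 1.96 × 0.50/√100 = 0.098. It reproduces. The SAP gives no precision figure for any JIA ACR comparison.

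**Inputs**
- n = 100: SAP 1.4 ("a sample size of approximately 100 subjects is thought to be sufficient to build a population PK model").
- Week 16 response rates as listed above. For JIA ACR 30, 0.873 × 173 = 151.0, so the rate fits a denominator of all 173 enrolled children.
- Antibody-positive share 40.1% (Protocol 1.1.2.2), taken as 40 against 60.
- Assumed, not in the documents: one normal underlying improvement scale, a two-sided 5% test, a correlation of 0.3, and a 0.5-SD shift. The SAP states "No statistical testing will be performed", so power here is only a yardstick for how well strata separate.

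**Step 1: counts.** 100 × (1 − 0.873) = 12.7 non-responders. With no antibody effect, 0.401 × 12.7 = 5.1 of them would be antibody-positive.

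**Step 2: information kept by the split** = φ(z)²/[p(1 − p)], where z is the normal quantile of p.
- JIA ACR 30: 0.2081²/(0.873 × 0.127) = 0.39
- JIA ACR 50: 0.2866²/(0.792 × 0.208) = 0.50
- JIA ACR 70: 0.3668²/(0.659 × 0.341) = 0.60
- JIA ACR 90: 0.3755²/(0.364 × 0.636) = 0.61

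**Step 3: concentration by response.** Simulated t-test of concentration between responders and non-responders, n = 100, correlation 0.3, 20,000 runs.

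**Step 4: response by antibody status.** The cut-point t solves 0.6Φ(t) + 0.4Φ(t − 0.5) = p, which keeps the overall rate at p. Power is from a two-proportion z-test with all outcomes enumerated, 60 against 40.

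| Endpoint | Step 3 power | Negative v positive, step 4 | Step 4 power |
|---|---|---|---|
| JIA ACR 30 | 46% | 91.5% v 80.9% | 39% |
| JIA ACR 50 | 56-57% | 85.0% v 70.5% | 44% |
| JIA ACR 70 | 65% | 73.3% v 54.8% | 48% |
| JIA ACR 90 | 66% | 43.7% v 25.5% | 47% |

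**Step 5: does the ranking depend on the model?**
- Common odds ratio 0.4, with the earlier rates as the antibody-negative level. For JIA ACR 30 the odds are 0.873/0.127 = 6.87; × 0.4 = 2.75; 2.75/3.75 = 73.3%. Power is 43% for JIA ACR 30, 60% for JIA ACR 70 (65.9% to 43.6%) and 48% for JIA ACR 90 (36.4% to 18.6%).
- The 0.5-SD shift, with the earlier rates as the antibody-negative level: 43%, 50% and 43% for JIA ACR 30, 70 and 90. The JIA ACR 70 gain remains and the JIA ACR 90 gain disappears.
- Equal absolute drop of 20 points: 67% for JIA ACR 30 (from 87.3%) against 51% for JIA ACR 70. The ranking reverses.

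**Step 6: titre.** Protocol 1.1.2.2 ties apparent efficacy loss to titres above 1:1000, seen in about 5% of children, which is 5/40.1 = 12.5% of positives. As an illustration, let only those children lose benefit:
- JIA ACR 30 falling from 89% to 50% in them gives 0.875 × 0.89 + 0.125 × 0.50 = 84% among all positives, power 11%.
- JIA ACR 70 falling from 65.9% to 25% gives 61%, power 8%.

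A positive/negative split misses such an effect at any response level.

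**The case against.** **Exposure-response does not rest on JIA ACR 30.** A reader might infer that it does. Protocol 9.3.3 and 11.6 and SAP 7.2 do not restrict the measure, so the point covers only the displays that the SAP specifies. These passages do not fill the gap for antibody status.

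**The rate here may be lower.** The earlier rates come from subcutaneous dosing. The Week 48 figures (89% to 95.9%) are observed-case data from a randomised-withdrawal phase that includes children on placebo, so they cannot be cited as open-label golimumab rates. Under SAP 5.1.2 a composite with every component missing counts as non-response. If 20 of 120 children were fully missing, 95.9% of the remaining 100 would become 95.9/120 = 80%. This stands, and it is why the figures above use Week 16. It bears less on the concentration plots, because children who stop treatment leave the by-visit concentration data (SAP 7.1.3).

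**The ranking is model-dependent.** This stands too (step 5). A common shift in underlying benefit is plausible but assumed.

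**The subgroup list is open-ended.** SAP 2.4.2 is not limited to its list, and all four levels by subtype and/or age are already planned. A reader might infer that subgroup work is locked to JIA ACR 30; the text does not say so.

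**Misreading is speculative.** Nothing in the SAP says flat rates will be taken as absence of effect, and the earlier study did report apparent efficacy reductions at high titre.

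**Conclusion.** The point holds for the two specified displays. If JIA ACR 30 is near 87% here and the effect acts as a common shift on one underlying scale, JIA ACR 30 is less sensitive than JIA ACR 70 or 90. The gap is about 46% against 65-66% for a concentration-response correlation of 0.3, and about 39% against 47-48% for a 0.5-SD antibody effect, both with n = 100. The antibody gain is modest, and for JIA ACR 90 it does not survive every calibration.

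A reader might infer that JIA ACR 30 can hardly separate the strata at all. That is too strong: at 87% the loss is moderate, large effects would still show, and no response level is precise at this sample size. For antibodies, changing the response level without using titre would leave the main weakness in place. The primary PK endpoint is unaffected. This is a cheap improvement to secondary, descriptive displays.

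**What to change.** - **SAP 7.3:** summarise JIA ACR 30, 50, 70 and 90 at Weeks 28 and 52 by antibody status and by titre category, including above 1:1000. Give 95% confidence intervals for the differences.
- **SAP 7.1.3:** draw the concentration box plots by JIA ACR 70 and JIA ACR 90 response as well as JIA ACR 30.
- **SAP 2.4.2 (optional):** add JIA ACR 70 to the subgroup summaries.

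The cost is SAP wording and a few extra tables and figures. All four response levels are already derived (SAP 5.4.2), and titres of confirmed positive samples are already reported (Protocol 9.3.4 and 11.5). No new data or visits are needed.

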Through Week 16 in CNTO148ART3001, 0.5% of subjects in the placebo group and 2.5% of subjects in the golimumab group had an infusion reaction. Through Week 112, 3.9% of golimumab-treated subjects had an infusion reaction and 0.4% of infusions were complicated by infusion reactions. It should be noted that all placebo infusions consisted of 0.9% normal saline alone rather than a true matched placebo. No serious infusion reactions requiring study agent discontinuation were noted. There was a case of anaphylaxis, which was not associated with study drug.

For the most comprehensive nonclinical and clinical information regarding golimumab, refer to the latest version of the Investigator's Brochure and Addenda for SIMPONI (golimumab).

The median peak serum golimumab concentration (ie, post-infusion golimumab concentration) of $41.56~\mu g/mL$ was observed at Week 4 following IV administration of 2 mg/kg golimumab at Week 0, Week 4, followed by q8w (±1 week) administration. This peak is higher than that reported for SC golimumab administration of 50 mg every 4 weeks (q4w). The median trough serum golimumab concentration in subjects receiving IV golimumab at 2 mg/kg q8w with MTX was $0.28~\mu g/mL$ at Week 12 and $0.22~\mu g/mL$ at Week 20; these levels are similar to those reported with SC golimumab 50 mg. Overall exposure to golimumab is approximately 3 times that for SC golimumab 50 mg over a similar period of exposure.

Data from the IV golimumab program demonstrated less radiographic progression in subjects treated with golimumab compared with subjects who received placebo. There was a significant difference in change from baseline in total van der Heijde Modified Sharp (vdH-S) score at Week 24 (placebo + MTX: 1.09 ± 3.194 , golimumab 2 mg/kg + MTX: 0.03 ± 1.899 [p<0.001]) between the golimumab + MTX treatment group and placebo + MTX. Significant differences in favor of IV golimumab were also observed in changes from baseline in erosion and joint space narrowing scores. The proportion of subjects with radiographic progression based on the smallest detectable change was significantly lower for subjects treated with golimumab + MTX when compared with placebo + MTX for the total vdH-S score (p<0.001) as well as both erosion (p=0.001) and joint space narrowing measurements (p=0.01).

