With regards to immunogenicity, 40.1% of subjects developed antibodies to golimumab using the recently developed drug tolerant immunoassay analyses. The new drug tolerant immunoassay is more sensitive compared with assays used previously in adult golimumab RA studies and allows the detection of antibodies to golimumab despite detectable serum golimumab levels. Among subjects who were randomized and remained on golimumab 30 mg/m² SC + MTX, 30.8% developed antibodies to golimumab; antibody titers tended to be low. When evaluating the effects of immunogenicity on PK, efficacy, and safety, it was found that positive anti-golimumab antibody status decreased steady-state trough golimumab concentrations when the titer levels were >1:100. However, the effect of antibodies on efficacy was less sensitive, requiring higher titers >1:1000 in order to correlate with apparent reductions in efficacy. Since only approximately 5% of subjects with JIA developed anti-golimumab antibodies with titers >1:1000, it was determined that immunogenicity was not a contributing factor to lack of achievement of the primary endpoint in CNTO148JIA3001. Additionally, positive anti-golimumab antibody status did not appear to be associated with a higher incidence of injection-site reactions.

The proportion of subjects who reported an AE through Week 48 was 87.9%. The most commonly reported SOC of AEs was Infections and infestations (67.1%), and were predominantly URTIs and nasopharyngitis. There was no marked difference in AEs reported between Week 16 and Week 48 for subjects randomized to placebo (82.9%) and those randomized to continued golimumab treatment (78.2%); however, it needs to be noted that all subjects in randomized withdrawal portion of the study were exposed to golimumab for

16 weeks before re-randomization. Serious adverse events were reported by 13.3% of subjects. The most commonly reported SAE was worsening of JIA (6.4%). Serious infections were reported in 2.9% of subjects (pneumonia, urinary tract infection, herpes zoster, URTI, and pyelonephritis), and there were no deaths, malignancies, or demyelination events through Week 48. There were no reports of active TB and no serious opportunistic infections. Through Week 48, the number of subjects with abnormal alanine aminotransferase (ALT) measurements (and no concomitant treatment for latent TB, which may affect liver function tests [LFTs]) was 29.5% (51/167), 39 of the 51 subjects had elevations <3×ULN.

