9.3.4. Immunogenicity Assessments (Antibodies to Golimumab)

Antibodies to golimumab will be evaluated in serum samples collected from all subjects according to the Time and Events Schedule (ie, Weeks 0, 4, 8, 12, 28, 52, 100, 148, 196, and 244). Additionally, serum samples should also be collected at the final visit from subjects who are discontinued from treatment or withdrawn from the study. These samples will be tested by the Sponsor or Sponsor's designee.

Serum samples will be screened for antibodies binding to golimumab and the titer of confirmed positive samples will be reported. Other analyses may be performed to verify the stability of antibodies to golimumab and/or further characterize the immunogenicity of golimumab.

The incidence of antibodies to golimumab during the study will be determined.

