1.2.2. Dosage and Administration

The study will have 1 active treatment group.

All subjects will receive 80 mg/m² golimumab (maximum single dose 240 mg) IV infusions at Week 0, Week 4, and q8w (±3 days) through Week 28 and q8w (±1 week) thereafter through Week 244. BSA will be calculated using the Mosteller equation:

BSA $(m^2) = ([height (cm) x weight (kg)]/3600)^{1/2}.$

All infusions will be completed over 30±10 minutes.

In addition, subjects will receive commercial MTX at the same BSA-based dose (10 to 30 mg/m² per week for subjects with BSA <1.67 m² or at least 15 mg/week for subjects with

BSA \geq 1.67 m²) as at time of study entry through Week 28. Absolute dose should remain stable from baseline through Week 28.

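### SAP 7.3 compares infusion reactions by child-level antibody status without requiring the reaction to follow the first positive sample, which dilutes a real link and can bias the Week 252 table in either direction

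*SAP*

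**What the plan says.** SAP 7.3 treats antibody status as a two-level attribute of the child: "The antibody status (positive, negative) of subjects will be summarized". Under the same heading it relates status to safety at the major assessment times, Weeks 28, 52 and 252, through "JIA ACR 30 responses by antibody to golimumab status; infusion reactions by antibody to golimumab status". It does not say whether positive means ever positive or positive at that visit. It has no timing rule linking a reaction to antibody onset, and no per-infusion denominator by status. Onset is handled as a separate item, "The onset of antibody to golimumab formation will be summarized", and is not tied to reactions.

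Other relevant provisions:
- SAP 6.2 and Protocol 9.4 define an infusion reaction as occurring during an infusion or within 1 hour of its end, so each reaction belongs to one infusion.
- Protocol 4.2, criterion 16, excludes children who have ever received golimumab.
- SAP 1.2.2 gives dosing as "IV infusions at Week 0, Week 4, and q8w (±3 days) through Week 28 and q8w (±1 week) thereafter through Week 244".
- Protocol 9.3.4 schedules antibody samples at "Weeks 0, 4, 8, 12, 28, 52, 100, 148, 196, and 244". The footnotes to the Time and Events Schedules require them to be drawn before that visit's infusion.
- SAP 5.1.1 states that there will be no statistical testing.

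**The concern.** A reaction is an event at one infusion, while antibodies appear some time after treatment starts. A label fixed for the whole period gives an antibody-positive child's early infusions and reactions to the positive column, although that child had no detected antibodies then. A child who reacts at Week 0 and first tests positive at Week 28 becomes an antibody-positive reactor.

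Two things follow. Within a fixed period, mixing pre-antibody and post-antibody infusions pulls a real association towards no difference. Over the long extension, both the chance of ever testing positive and the chance of ever reacting grow with time on treatment, so unequal follow-up can distort an ever-positive table. Whether antibodies go with infusion reactions is a natural safety question for an intravenous product in children, and SAP 7.3 specifically plans to address it. With so few reactions expected, one misplaced event can change what the table appears to say.

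**Working it through.** The SAP gives no figure for this comparison. Its only precision figures (Table 1, mean concentration) reproduce, for example 1.96 × 50% / √100 = 9.8%, but do not bear on it.

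**Inputs from the documents.** Infusions at Weeks 0, 4, 12, 20, 28 and then every 8 weeks: 5 through Week 28 and 32 through Week 244. As a guide to reaction frequency, the adult IV study (Protocol 1.1.2.1) reports that "0.4% of infusions were complicated by infusion reactions" through Week 112, with 2.5% of golimumab subjects reacting by Week 16. As a guide to antibody frequency, in the subcutaneous JIA study (Protocol 1.1.2.2) "40.1% of subjects developed antibodies to golimumab" (30.8% in those kept on drug). Planned size is 120, with 20 lost by Week 52.

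**Assumptions.** True ratio 1 or 3. Antibody onset complete by Week 12, spread to Week 48, or at a constant hazard giving 40.1% by Week 48. Dropout of 1 in 6 per year after Week 52. Reaction rate flat at 0.4% per infusion, or front-loaded. Front-loading is suggested by 2.5% / 3 infusions ≈ 0.8% per infusion by Week 16, against 0.4% through Week 112.

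**Step 1: infusions before the first positive sample, through Week 28.** With p = 0.004 and true ratio 3, the child-level ratio is [1 − (1−p)^pre × (1−3p)^post] / [1 − (1−p)^5]. The denominator is 1 − 0.996^5 = 0.0198.

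| First positive | Pre / post | Positive child's risk | Ratio shown |
|---|---|---|---|
| Week 4 | 1 / 4 | 0.0510 | 2.6 |
| Week 8 or 12 | 2 / 3 | 0.0433 | 2.2 |
| Week 28 | 4 / 1 | 0.0277 | 1.4 |

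These ratios do not depend on how many children become positive. Simulated over the onset patterns, a true 3 shows as about 1.5 to 2.3 at Week 28. The upper end is early onset with a flat rate; the lower end is later onset with front-loaded reactions.

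**Step 2: number of events.** 120 × 0.0198 = 2.4 reacting children by Week 28 at the flat rate, or 120 × 2.5% = 3 at the adult Week 16 figure. With 48 positive (40.1% of 120) and 72 negative children and a true ratio of 3, Fisher power is 6% with 2 of 5 infusions misassigned and 13% with none.

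**Step 3: Week 252, ever-positive table, no true link.**

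| Scenario | Ratio shown |
|---|---|
| Complete follow-up | 1.0 |
| Dropout unrelated to reactions, onset ends by Week 12 or 48 | 1.05 to 1.18 |
| Same dropout, constant onset hazard to Week 244 | 2.1 to 2.3 flat; about 1.5 front-loaded |
| Every reaction ends treatment (extreme) | 0.25 to 1.0 |
| Children still on study, dropout unrelated to reactions | 1.0 |

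The high value arises because positive children average 25.3 infusions and negative children 11.6. It needs the hazard to run on unchanged, which implies 1 − 0.599^(244/48) = 93% positive by Week 244.

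**Step 4: candidate replacements.** Classifying each infusion by the latest sample on or before it recovers about 1.0 and 3.0 when the rate is flat. If reactions are front-loaded, that crude ratio falls to 0.44 to 0.81 with no true link, because early infusions are nearly all pre-antibody. Stratifying by infusion number gave 1.0 and 3.0 in every scenario.

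**The case against.** The strongest reply is that status may mean the result at the assessment visit. SAP 7.3 uses visit-specific wording when it compares Week 28 with Week 52 status, and ever-positive is nowhere written. This has force for Week 252: if the table covers only children still on study, follow-up is equal and the spurious ratio disappears when dropout is unrelated to reactions. It does not cure the dilution, since the tabulated reactions still mostly precede the sample. It also leaves Week 252 undefined for completers, whose last scheduled sample is Week 244.

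The comparison is also descriptive, events are rare, and SAP 6.2 adds average follow-up and average number of infusions to all AE summary tables. Rarity does limit the Week 28 table more than classification does. Average infusions may expose unequal exposure, but they do not show whether a reaction came before or after antibodies.

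A reader might infer that the plan hides a real link at Week 28 and manufactures a false one by Week 252. The documents support neither. The early link shrinks but does not vanish. The late one needs continuing antibody onset together with unequal follow-up, and Protocol 1.1.2.2 gives a proportion positive, not a hazard to extend to Week 244. Stopping after severe reactions (Protocol 9.4, 10.2) can push the ratio below 1.

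Finally, a plain per-infusion table could be worse than the planned one when there is no link. That is correct, and it shapes the fix.

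**Conclusion.** The point stands as a gap in SAP 7.3. Antibody status is not defined in time, and reactions are not ordered against it. That pre-antibody infusions are counted as positive follows from the schedule and the exclusion of prior golimumab; no modelling is needed. The resulting dilution at Week 28 appeared under every onset and reaction pattern tried.

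The Week 252 bias is a possibility of uncertain direction, not a predicted result. Its size rests on onset and extension-dropout patterns that the documents do not give, and on adult intravenous and paediatric subcutaneous rates used only as guides. The change is worth making because it is cheap and makes the few observed reactions interpretable; it will not make the comparison well powered.

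**What to change.** Amend SAP 7.3 as follows:
- Classify each infusion by antibody status at the latest sample on or before it, positive from the first confirmed positive sample.
- Replace the child-level reaction table with infusions with a reaction divided by infusions given, by that status. Stratify by infusion number or study period, for example Week 0, Weeks 4 to 12, and later. Do not present the crude ratio alone.
- List every reaction with its date relative to the child's first positive sample, or mark the child as never positive.
- State that the Week 252 table uses samples through Week 244, or the safety follow-up visit for children who stopped treatment.

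The cost is SAP wording, one reprogrammed table and one listing. Infusion records, reaction records and sample dates are already collected (Protocol 7, 9.4, 9.5). There are two small downsides. Antibody sampling is sparse, so some infusions between the last negative and the first positive sample will be classed as negative. The strata will also be thin, so the listing may be the most informative output.
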